Effect of PVP-I Nasal Sprays vs Normal Saline Nasal Sprays on
SARS-CoV-2 Nasopharyngeal Titers

NCT04347954

Document Date: July 10, 2020

Background Summary

Human transmission of SARS-CoV-2 (COVID-19) occurs primarily through droplet spread into the nose and mouth. Arresting COVID-19 replication after infection of the nasal tissues specifically would decrease the duration and severity of infection in COVID-19-exposed patients, and may significantly impact COVID human to human transmission. Povidone-iodine (PVP-I) solution is a widely available, inexpensive antiseptic medication, used in the surgical theater to reduce the incidence of surgical wounds and intranasally to reduce MRSA colonization. However, the role of PVP-I in the treatment of nasal infections is limited. Interestingly, prior in vitro studies have demonstrated dilute PVP-I solutions, in concentrations as low at 0.23%, produce a ≥ 4 log10 decrease (inactivation of $\geq 99.99\%$) in SARS and MERS virus titers within 15 seconds.^{1,2} Both viruses share high structural overlap with COVID-19. A study of 29 patients with recalcitrant sinusitis found reduced bacterial growth with good safety profile after use of 0.08% PVP-I nasal rinses.³ PVP-I nasal sprays of up to 4.4% concentration have also been used on healthy volunteers without adverse effects or nasal tissue damage.⁴ In Wuhan, China, PVP-I was recently used empirically by healthcare providers devoid of COVID-19 protection, given its ease of use, and potential for mitigating infection. Given this encouraging background, and current world events, we propose testing dilute PVP-I sprays as a topical treatment to directly ablate COVID infection within the nasal cavity.

Specific aims

1. To determine if PVP-I nasal sprays reduce viral shedding in the nasopharynx and nasal cavity
 - a. Hypothesis 1: PVP-I nasal sprays will reduce viral shedding in the nasopharynx and nasal cavity as determined by PCR testing when compared to control groups
2. To determine if PVP-I nasal sprays affect the severity and time to resolution of signs and symptoms of COVID-19
 - a. Hypothesis 2a: PVP-I nasal sprays will not change the severity or time to resolution of systemic signs and symptoms (such as fever, fatigue) when compared to control groups
 - b. Hypothesis 2b: PVP-I nasal sprays will reduce the duration of anosmia symptoms when compared to control groups
3. To determine adverse effects of PVP-I nasal sprays
 - a. Hypothesis 3: PVP-I nasal sprays will not be associated with a greater rate of adverse effects as compared to the control groups

Methods

Overview of study design

This is a prospective, double-blind, placebo controlled, randomized control trial of COVID-19 positive patients that has three study arms.

Arms:

- (1) 2% povidone iodine nasal spray – two sprays to each nare four times a day for 5 days
- (2) 0.5% povidone iodine nasal spray – two sprays to each nare four times a day for 5 days
- (3) Control – Dyed normal saline (0.9% NaCl) spray – two sprays to each nare four times a day for 5 days

Study population: COVID-19 positive inpatients and outpatients

Inclusion criteria:

1. ≥ 18 years ago
2. Diagnosis of COVID-19 by lab test within 5 days of study participation

Exclusion criteria:

1. Allergy to "iodine," shellfish, or food dye
2. Receiving intranasal steroids
3. Sinus surgery within 30 days of beginning the study
4. Intubated at the time of enrollment
5. Pregnancy
6. Participation in other COVID-19 studies - to be determined on a case by case basis

Measurements/Outcomes

The primary outcome measure is the viral load on nasopharyngeal swab determined by quantitative PCR testing. A baseline sample (Day 1) will be obtained prior to first administration of the sprays. Subsequent samples will be collected at 4 hours after first administration and on day 5 after initiating nasal sprays.

Intake questionnaire – dates of symptom onset, comorbid conditions, specific questions regarding taste and smell disturbances

Patient reported symptoms (completed on Day 3 and Day 5) – fever, fatigue, change or loss of sense of smell, change or loss of sense of taste, nasal congestion, sore throat, etc

Adverse effects questionnaire (completed on Day 3 and 5) – Nasal burning/pain, headaches, ear pain, sneezing, nose bleeds, rash

University of Pennsylvania Smell Identification Test (completed on day 1 and day 30) – to assess smell recovery in COVID-19 patients

Statistics

T-test or ANOVA to compare difference in mean viral load between groups. Chi-square to assess for differences in signs, symptoms, adverse effects.

Sample size: 45 subjects (15 subjects per study arm)

Study Procedures - Outpatient

Recruitment strategy

In terms of advertising to the general public, we will send out flyers for general distribution on social media (e.g., Facebook, Nextdoor, etc) that will allow interested persons in the general public to contact our team. Our social media advertising strategy is being developed in conjunction with StudyPages, a clinical trial recruitment company recommended by the Stanford Research Participation Program.

Moderation of Facebook and other social media posts will be conducted as outlined in a separate

attached document and includes daily monitoring of comments and hiding/deletion of protected health information. Prospective participants can opt to have their contact information sent to the team.

Potential subjects who have expressed interest in being contacted about research studies will be contacted by phone by one of the investigators. The study will be described, patients will have the opportunity to ask questions, and if they wish to proceed, they will be given details on their first in person study visit.

Prospective participants that have undergone telephone screening will come to the clinic parking lot at [name] or the Galvez lot at the designated date and time. At this in person study visit, the study will be reviewed again and the consent form signed if the patient still wishes to proceed. Randomization will take place. This will count as Day 1 of the study.

Active Phase

Given the known COVID-19 positive status, we are putting in place the following procedure for in person study visits. For first study visits scheduled on a Saturday, subjects will drive to the [name] parking lot which is the parking lot associated with the Department of Otolaryngology's clinics. We have approval from the department chair and clinic leadership to use the parking lot. Participants will remain in their vehicle with the window rolled down for necessary study procedures. Return visits on day 5 will be scheduled for times either before 8 am or after 5 pm. Privacy will be ensured in several ways. First, the parking lot is behind the building and thus not visible from the main road. Second, we will be using moveable plastic barriers during study procedures to protect privacy. Lastly by having subjects only come in outside normal clinic hours (Saturday or pre/post-clinic), this will minimize the presence of other persons.

We have also received approval from [name] who is the Operations Manager of the Galvez research lot to utilize the tent space or the parking lot space at this site for study procedures. Weekday study procedures will take place at this site ([name]).

Participants will complete the first questionnaire and take the University of Pennsylvania Smell Identification Test (UPSIT) on the day of enrollment. This is a multiple-choice scratch and sniff test that is self-administered. A baseline nasopharyngeal sample will be taken. Next the first dose of the nasal spray will be given. Subjects will have the option to stay or return for the four hour sample collection timepoint. Four hours later, a member of the research team will obtain the 4-hour post-administration nasal sample. Subjects will then return home. Participants will be given (physical or electronic) a gift card for \$25 at the end of the day.

Participants will continue to self-administer the spray as instructed while at home. They will also take daily symptom questionnaires administered through REDCap. Participants will return for a drive-through nasal swab at [name] or at the Galvez lot on Day 5.

On day 30, participants will complete an UPSIT, self-administered smell test, which will be given to patients with a self-addressed, pre-paid envelope to return.

Close Out

The study medication will be discontinued on Day 5. The second gift card (\$25) will be mailed either through the postal service or through email to participants approximately 30 days after the first study visit upon completion of the final UPSIT.

Specimen Handling

Each sample will be labelled with a subject's unique record ID number. These samples will be processed in the Stanford clinical virology lab (permission has been obtained from [name]) and results associated with a given record ID number in REDCap.

Payment/Reimbursement

Participants will be given a total of \$50 in gift cards if they complete the study. They will receive a \$25 gift card at the end of the first in person study visit. If they complete the remaining in person visits on Days 5, they will be mailed (either via postal service or email) the second \$25 gift card along with the final smell test.

Safety of proposed treatment arms

A small quantity of food dye is commonly used on mucosa membranes in the head and neck in routine clinical practice for instance to assess for fistula or to assess swallow function.⁵ It has also been used in numerous prior research studies assessing the distribution of drug delivery methods in the nasal cavity.⁶ There is no added risk to including this in the control group saline solution.

PVP-I solutions are routinely used as mouth washes with minimal absorption through the mucus membranes.⁷ Additionally, iodine solutions are used in the nose for MRSA decolonization and have been used long term in nursing home residents.⁸ Furthermore, prior studies have used concentrations as high as 4.4% in nasal spray form for extended periods in healthy volunteers without adverse effects.⁴ In our clinical practice, 10% PVP-I is used in the mouth and nose as a surgical prep prior to procedures in the operating room. Additionally, some of our patients with chronic sinus disease have been instructed to use high volume (240 mL) nasal rinses of PVP-I for several months without observed adverse effects or objective changes on nasal endoscopy.

With long term use of iodine containing compounds, there is a theoretical risk of excessive iodine absorption which could affect the thyroid gland. However, given the short duration of our study, the cumulative exposure will remain far lower than in many common medical procedures.

0.5% PVP-I contains 5 mg/mL and 2% PVP-I contains 20 mg/mL. The estimated volume delivered by two nasal sprays to each nare in a single administration is 0.33 mL.⁹

0.33 mL/dose x 4 doses/day x 7 days = 37.2 mL of solution administered.

At a 0.5% PVP-I concentration, the total amount of iodine administered is 186 milligrams. At 2.0% PVP-I, the total amount of iodine administered is 744 milligrams or 0.744 grams. The most common medical procedure in which patients are exposed to iodine are computed tomography (CT) scans which use iodinated contrast. The average dose per scan is estimated to be 15-37 grams of iodine¹⁰ which is an order of magnitude greater exposure to iodine than what is proposed in this study.

Participant study timeline

Day 0	Enrollment, intake questionnaire, baseline NP swab, first dose of sprays, 4-hour post NP swab, UPSIT
Day 1	Continue sprays
Day 2	Continue sprays, symptom questionnaire, adverse symptoms and compliance questionnaire
Day 3	Continue sprays, daily questionnaire

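### Aim 2 asks how long symptoms and anosmia last, but questionnaires stop on the last spray day, the Day 30 smell test has no stated analysis, and chi-square is the only symptom test

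*Combined protocol and SAP*

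**What the plan says.** The Specific aims section states Aim 2 as "To determine if PVP-I nasal sprays affect the severity and time to resolution of signs and symptoms of COVID-19". Hypothesis 2a predicts that "PVP-I nasal sprays will not change the severity or time to resolution of systemic signs and symptoms", and gives no margin. Hypothesis 2b is "Hypothesis 2b: PVP-I nasal sprays will reduce the duration of anosmia symptoms when compared to control groups".

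Measurements/Outcomes provides:

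- an intake form covering "dates of symptom onset, comorbid conditions, specific questions regarding taste and smell disturbances";
- "Patient reported symptoms (completed on Day 3 and Day 5";
- "University of Pennsylvania Smell Identification Test (completed on day 1 and day 30".

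The outpatient Active Phase section instead describes daily REDCap symptom questionnaires and gives no end date. The Participant study timeline lists symptom or daily questionnaires on its Days 2, 3 and 4, the last being the final spray day. It lists no procedures for Days 6 to 29, and then the repeat UPSIT on Day 30.

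On analysis, the Statistics section says "Chi-square to assess for differences in signs, symptoms, adverse effects" and assigns the t-test or ANOVA to viral load only. The size is given as "Sample size: 45 subjects (15 subjects per study arm".

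**The concern.** Time to resolution and duration of anosmia are time-to-event quantities. Estimating them needs observation until most participants have resolved, a definition of resolution, and a method that handles those who have not. The plan has none of the three.

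Followed exactly, it would give a chi-square on whether a symptom is present at a questionnaire. At the last questionnaire, that tells us whether the symptom had gone about 4 days after baseline, not how long it lasted. Smell loss that ends between that form and Day 30 is known only to have ended somewhere in the gap (interval-censored). Loss still present at Day 30 is right-censored.

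There is a second risk. Hypothesis 2a predicts no change. With 15 per arm and a few days of data, a non-significant chi-square is likely even if an effect exists, and it could be reported as confirmation.

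The severity part of Aim 2 is not at issue here.

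**Working it through.** **Schedule.** The text counts baseline as Day 1; the timeline counts it as Day 0.

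| Source | Post-baseline symptom forms, as written | In the text's numbering | Number |
|---|---|---|---|
| Measurements/Outcomes | Days 3, 5 | Days 3, 5 | 2 |
| Active Phase (outpatient) | daily, no end date | Days 2–5 if stopped with the sprays | at most 4 |
| Participant study timeline | Days 2, 3, 4 | Days 3, 4, 5 | 3 |

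- Baseline to last form: 5 − 1 = 4 elapsed days (text); 4 − 0 = 4 (timeline).
- Last form to Day 30 UPSIT: 30 − 5 = 25 days (text); 30 − 4 = 26 (timeline).

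**Analysis.** The Statistics section gives no time-to-event method, censoring rule, definition of resolution or UPSIT analysis. It does not say whether symptom comparisons use all participants or only those with the symptom at intake. This matters because smell loss is not an inclusion criterion.

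**Size of the loss (illustrative).** The documents give no anosmia duration, effect size or alpha. The assumptions are:

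- exponential recovery from baseline, with control median *m* = 7, 14 or 21 days;
- recovery hazard ratio (HR) 2;
- one PVP-I arm against control, with all 15 per arm anosmic;
- two-sided 5%;
- Day 30 = 29 elapsed days.

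With λ = ln 2 / *m*, the share of controls recovered by day *t* is 1 − exp(−λ*t*); in the PVP-I arm it is 1 − exp(−2λ*t*).

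| Control median (days) | 7 | 14 | 21 |
|---|---|---|---|
| Controls recovered by 4 days | 0.327 | 0.180 | 0.124 |
| Controls recovering in the gap (4 to 29 days) | 0.616 | 0.582 | 0.492 |
| Controls not recovered at Day 30 | 0.057 | 0.238 | 0.384 |
| Recoveries in both arms by the last form | 13.1 | 7.6 | 5.3 |
| Log-rank power on those | 24% | 16% | 12% |
| Recoveries in both arms by Day 30 | 29.1 | 25.6 | 22.0 |
| Log-rank power if followed to Day 30 | 46% | 42% | 37% |
| Same, if half of each arm is anosmic | 26% | 24% | 21% |

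Example for *m* = 7 at 4 days: control 0.327, PVP-I 0.547, so expected recoveries = 15 × (0.327 + 0.547) = 13.1. Power (Schoenfeld) = Φ(√(13.1/4) × ln 2 − 1.96) = 24%.

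Events for 80% power at HR 2 with 1:1 allocation: 4 × (1.96 + 0.84)² / (ln 2)² = 65.3, so 66. A two-arm comparison has at most 30 participants.

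**The Day 30 UPSIT as the alternative endpoint.** The difference detectable with 80% power is 2.80 × √(2/*n*) × √(1 − *r*²) SD, where *r* is the assumed correlation between Day 1 and Day 30 scores.

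| Impaired per arm | *r* = 0 | *r* = 0.5 |
|---|---|---|
| 15 | 1.02 SD | 0.89 SD |
| 8 | 1.40 SD | 1.21 SD |

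**The case against.** The strongest reply is that the data are heavily censored, not absent. Onset dates are collected at intake, and the questionnaires would support a right-censored analysis of early resolution once a method is named. That is true, but no such method is stated, and most of the assumed anosmia recoveries would still fall outside the window.

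Other points stand in part:

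- **Schedule.** After a one-day shift, the timeline's adverse-effect forms line up with Days 3 and 5 in the text, and the daily REDCap sentence sits under outpatient procedures only. The symptom schedules still differ (Days 3 and 5; daily; Days 3, 4 and 5), and none places a form after the sprays end.
- **Day count.** Measurements/Outcomes places the last swab on day 5 after starting the sprays, which could mean 5 elapsed days. The shares of controls recovering in the window would then be 39%, 22% and 15%, with about 15, 9 and 6.5 recoveries. The conclusion is the same.
- **Faster symptoms.** The medians above are for anosmia. With an assumed control median of 4 days, half of controls resolve in the window, about 19 resolutions are seen, and power is 32% against 47% with follow-up to Day 30. The loss is smaller for systemic symptoms that clear quickly.
- **UPSIT.** A dichotomised score might be read as a sign covered by the chi-square. The plan does not say so, and it would still describe status at Day 30 rather than duration.
- **Importance.** This is a secondary aim in a 45-person trial whose primary outcome is viral load. That limits the consequence but does not make the hypothesis answerable.

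**Conclusion.** The concern holds. The mismatch between Aim 2 and the plan is visible in the text and needs no assumption: observation ends about 4 days after baseline, a gap of 25 or 26 days follows, and the stated test estimates no duration. How much information is lost depends on the assumed exponential recovery, medians and hazard ratio. On those, about 13, 8 or 5 recoveries are observed in one arm plus control, against 29, 26 or 22 with questionnaires to Day 30. This should be fixed, but it does not affect the primary outcome.

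**What to change.** Choose one of two routes.

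**(a) Keep the duration question.** Continue the REDCap questionnaire, daily or every 2–3 days, until resolution or Day 30, for all participants. Define resolution and take randomisation as the time origin. Among participants with the symptom at intake, analyse time to resolution by Kaplan–Meier and log-rank, or by interval-censored methods, and report estimates with confidence intervals. The cost is a minor amendment and a slight participant burden, with no extra visit. Power remains low: 37–46% at HR 2 if all are anosmic, and 21–26% if half are.

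**(b) Change the question.** Restate Hypothesis 2b as smell recovery at Day 30 and remove duration and time to resolution from Aim 2. Analyse the Day 30 UPSIT score by ANCOVA adjusted for the Day 1 score, among participants impaired at baseline by a pre-specified Day 1 cut-off. Give an estimate and confidence interval for each PVP-I arm against control. No new data are needed, but the hypothesis is narrower and only large differences are detectable (about 0.9–1.0 SD with 15 impaired per arm, 1.2–1.4 SD with 8). Postal non-return of the Day 30 test would reduce these numbers further.

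Under either route, reconcile the three questionnaire schedules and the Day 0/Day 1 numbering, label the aim exploratory, and state that a non-significant result does not support Hypothesis 2a. Neither route makes 2a testable, because it has no margin.

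### Hypotheses 3 and 2a claim no increase and no change, but the only planned analysis is a chi-square for differences at 15 per arm, which can contradict them but cannot support them

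*Combined protocol and SAP*

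**What the plan says.** Two of the hypotheses under Specific aims are claims of absence. Hypothesis 3 reads "PVP-I nasal sprays will not be associated with a greater rate of adverse effects as compared to the control groups". Hypothesis 2a reads "PVP-I nasal sprays will not change the severity or time to resolution of systemic signs and symptoms", with fever and fatigue as examples.

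The aims above them are neutral: "To determine adverse effects of PVP-I nasal sprays" for Aim 3 and "To determine if PVP-I nasal sprays affect the severity and time to resolution of signs and symptoms of COVID-19" for Aim 2.

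The Statistics section has one sentence on these outcomes: "Chi-square to assess for differences in signs, symptoms, adverse effects". Its other analysis sentence, on t-test or ANOVA, concerns viral load only. The sample size is 45, or 15 per arm, with no derivation. Nowhere do the documents give a margin, a confidence interval, a significance level, an expected event rate or a rule for reading a non-significant result. They also do not say whether the chi-square compares all three arms, each PVP-I arm with saline, or the two PVP-I arms pooled with saline.

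**The concern.** A test for differences takes equality as its null hypothesis. A significant result can contradict Hypothesis 3 or 2a, but a non-significant one only fails to reject equality. With 15 per arm, failing to reject is the likely outcome even when a moderate rise is real. A p-value alone does not show whether a relevant rise has been excluded or simply not seen.

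Hypothesis 3 is also directional (no greater rate), whereas a chi-square across arms has no direction. For Hypothesis 2a the gap is wider, because a chi-square on proportions does not analyse time to resolution.

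What is at stake is the tolerability conclusion and the no-change conclusion on systemic symptoms. The primary analysis of viral load is not affected.

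**Working it through.** **Inputs.** From the documents: three arms of 15 (3 x 15 = 45, so the stated total is consistent) and six listed adverse effects. Assumed, because the documents give none: two-sided 0.05, no dropout, uncorrected Pearson chi-square, and the event rates below. There is no stated power or effect size, so 15 per arm can be neither reproduced nor refuted.

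**Step 1: power.** Each arm's count is Binomial(15, p). All combinations of three counts were enumerated, and the probabilities of those with p ≤ 0.05 were summed. Rates are in the order 2% / 0.5% / saline.

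| True rates (%) | 3x2 test | 2% v saline | Pooled PVP-I v saline |
|---|---|---|---|
| 30/10/10 | 0.270 | 0.278 | 0.102 |
| 30/30/10 | 0.233 | 0.278 | 0.338 |
| 40/10/10 | 0.524 | 0.510 | 0.204 |
| 50/10/10 | 0.761 | 0.726 | 0.335 |
| 50/50/10 | 0.713 | 0.726 | 0.823 |

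The chance of a miss is 1 minus power. For a rise from 10% to 30% in the 2% arm only, it is 1 - 0.270 = 73% (3x2) and 1 - 0.102 = 90% (pooled, because the pooled rate is then (30 + 10)/2 = 20% against 10%). With the rise in both PVP-I arms, it is 77% (3x2) and 66% (pooled). A fourfold rise in one arm (40/10/10) is found by the 3x2 test about half the time. Rises to 50% against 10% are found 71% to 76% of the time by that test.

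**Step 2: sparse cells.** With equal arms, the expected events per arm are the total divided by 3, so expected counts are below 5 whenever there are fewer than 15 events in all. At 30/10/10 the expected total is 15 x (0.3 + 0.1 + 0.1) = 7.5, or 2.5 per arm. Of the five settings in the table, only 50/50/10 exceeds 5 per arm (16.5/3 = 5.5). Fisher's exact test for 30% v 10% has 15% power, against 28% for the uncorrected chi-square.

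**Step 3: what a bare p-value hides.** Take 6, 2 and 2 events. Each arm has 10/3 = 3.33 expected events and 35/3 = 11.67 expected non-events.

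- Chi-square = [(6 - 3.33)² + 2 x (2 - 3.33)²] x (1/3.33 + 1/11.67) = 10.67 x 0.386 = 4.11. On 2 df, p = exp(-4.11/2) = 0.128.
- 2% v saline is 6/15 - 2/15 = 0.267. The Wilson limits are 0.198 to 0.643 and 0.037 to 0.379.
- Newcombe lower limit: 0.267 - √[(0.400 - 0.198)² + (0.379 - 0.133)²] = -0.05.
- Newcombe upper limit: 0.267 + √[(0.643 - 0.400)² + (0.133 - 0.037)²] = +0.53.

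The test is non-significant, yet the data allow a rise of up to 53 points. With identical counts of 2/15 and 2/15 (p = 1), the interval still runs from -26 to +26 points.

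**Step 4: whether a formal no-increase claim is within reach.** With equal true rates p, one-sided 0.025 and 80% power, the margin that n per arm can exclude is (1.96 + 0.84) x √[2p(1 - p)/n]. At n = 15 this is about 31, 41 and 47 points for p = 10%, 20% and 30%. Excluding 20 points would need 36, 63 and 83 per arm. Estimation is realistic at this size; a formal claim is not.

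**Step 5: symptom timing (Hypothesis 2a).** Measurements/Outcomes places the symptom form on Days 3 and 5. Active Phase says daily. The Participant study timeline lists symptom or daily forms on Days 2, 3 and 4, in a numbering that starts at Day 0, whereas Recruitment strategy counts the enrolment visit as Day 1. Moving the timeline on by one day turns its Days 2 and 4 into Days 3 and 5, but the conflict between daily and two-day collection remains. The timeline then shows no procedures on Days 6 to 29.

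**The case against.** The best defence is that Hypotheses 2a and 3 are predictions under neutral aims, and that a test for differences suits those aims. This stands for the aims. It does not supply a way to support the hypotheses as worded.

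A reader might infer that the sponsor intends to declare the sprays safe if the test is non-significant. The documents do not say so; they are silent on how such a result will be read. A reader might also infer that the trial cannot detect harm at all, or that it must become a non-inferiority trial. Neither follows. A rise from 10% to 50% is found more often than not by the 3x2 test, and nothing in the neutral aims calls for a formal margin.

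It can also be said that anyone given the counts can compute an interval. That is true if counts are published by arm, but the plan does not commit to this, and the comparison to be estimated is better fixed in advance.

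Finally, intervals will not separate safe from missed very well. With truly equal rates of 5% to 30%, 67% to 74% of trials with a non-significant 3x2 test still have an upper limit of +20 points or more for 2% v saline. This stands. It is a reason for estimation wording and a modest conclusion, not for a bare test.

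**Conclusion.** The mismatch is real and limited. As planned, the analysis of adverse effects and systemic symptoms can contradict Hypotheses 3 and 2a but can never support them, and no rule says what a non-significant result means. Under the assumed rates, a tripling from 10% to 30% goes undetected in about two thirds to nine tenths of trials by the 3x2 or pooled test, depending on the form of the test and on whether one or both PVP-I arms are affected. All of these figures rest on assumed rates, two-sided 0.05 and the uncorrected test; an exact test would miss more. Both hypotheses are secondary to viral load, so this should be changed but does not threaten the primary result.

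**What to change.** 1. **Hypothesis 3.** Make the main result the risk difference of each PVP-I arm v saline with a 95% CI (for example Newcombe), for any listed adverse effect over the treatment period and for each of the six listed effects. Note that headache and sneezing may also be symptoms of the illness.
2. **Hypothesis 2a.** Report the same risk differences with CIs for systemic symptoms at the scheduled questionnaires. State that this describes symptom presence only: it does not analyse time to resolution, and resolution after Day 5 is not observed. Reconcile the sections that give different questionnaire days and day numbering.
3. **Wording.** Recast both hypotheses as estimation aims, in line with Aims 2 and 3, and state that a non-significant test will not be taken as evidence of no increase or no change.
4. **If a test is kept as support.** State its form (3x2, pairwise or pooled), use an exact test where expected counts are below 5, and say that the six items are not adjusted for multiplicity. With two uncorrected pairwise tests, the chance of at least one false signal per item is about 5%, 9% and 10% at common rates of 10%, 20% and 30%. Over six items, if independent, 1 - (1 - 0.0455)⁶ = 24%, and likewise 43% and 47%.

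**Cost.** The change is wording and a few lines of analysis on forms already planned, plus the schedule reconciliation; it needs no extra patients, visits or samples. The intervals will be wide (mean half-width about 23 to 31 points if rates are equal), an exact test gives up some power, and the safety conclusion becomes more modest.

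### No pre-spray record is listed for fever, fatigue, nasal congestion or sore throat, so Aim 2 loses precision on these symptoms and time to resolution has no defined starting group

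*Combined protocol and SAP*

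**What the plan says.** Aim 2 (Specific aims) is "To determine if PVP-I nasal sprays affect the severity and time to resolution of signs and symptoms of COVID-19". Hypothesis 2a states that "PVP-I nasal sprays will not change the severity or time to resolution of systemic signs and symptoms (such as fever, fatigue) when compared to control". Hypothesis 2b states that "PVP-I nasal sprays will reduce the duration of anosmia symptoms when compared to control groups".

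The symptom form appears in three places:

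- **Methods, Measurements/Outcomes:** "Patient reported symptoms (completed on Day 3 and Day 5) – fever, fatigue, change or loss of sense of smell", followed by taste, nasal congestion, sore throat and others. The baseline swab is taken on Day 1 before the first spray.
- **Study Procedures - Outpatient, Active Phase:** after the first dose, the 4-hour sample and the return home, "They will also take daily symptom questionnaires administered through REDCap".
- **Participant study timeline:** enrolment is Day 0 and has an intake questionnaire, swabs, the first dose and the smell test. The first symptom questionnaire is on Day 2.

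Two instruments are described before the first dose. One is "Intake questionnaire – dates of symptom onset, comorbid conditions, specific questions regarding taste and smell disturbances". The other is "University of Pennsylvania Smell Identification Test (completed on day 1 and day 30".

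The entry line reads "Study population: COVID-19 positive inpatients and outpatients". The Statistics section plans a chi-square test for signs and symptoms, with 15 participants per arm. It mentions no baseline adjustment and no symptom score.

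**The concern.** Hypothesis 2a is about systemic symptoms such as fever and fatigue. As listed, the data on these symptoms begin after treatment has begun. A participant without fever at the first symptom form may have lost it on the spray, lost it before enrolment, or never had it. An onset date does not separate the first two cases.

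Three things are at stake for these symptoms. Change from entry cannot be calculated. A chance difference between small arms at entry cannot be detected or allowed for. Time to resolution, which Aim 2 names, has no documented group of participants who had something to resolve. Hypothesis 2a also predicts no difference, so an imprecise comparison makes the predicted finding easier to obtain and harder to interpret.

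**Working it through.** **1. Is there a symptom form before the first spray?**

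| Source | Enrolment day called | First symptom form | Before first spray? |
|---|---|---|---|
| Measurements/Outcomes | Day 1 | Day 3 | No |
| Active Phase | Day 1 | Daily, described after the first dose | No |
| Participant study timeline | Day 0 | Day 2 | No |

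Day 2 counted from 0 is Day 3 counted from 1, so the first and third rows agree on the first form. The sources differ on frequency and numbering, but none has a form before the spray.

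**2. Do the pre-spray instruments fill the gap?**

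| Symptom | Listed pre-spray data on presence or severity |
|---|---|
| Smell | Intake questions; Day 1 smell test |
| Taste | Intake questions |
| Fever, fatigue, nasal congestion, sore throat | None (symptom onset dates only) |

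The Active Phase text describes the first questionnaire and the smell test ahead of the first dose. The gap is therefore confined to the last row.

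**3. Size of chance imbalance at entry.** The plan gives no symptom rates and no power calculation, so there is no figure to reproduce beyond 3 × 15 = 45. Input from the plan: n = 15 per arm. Assumption: prevalence p at entry of 30, 50 or 70%. Let X1 and X2 be independent Bin(15, p). Then P(|X1 − X2| ≥ k) is the sum of P(X1 = a)·P(X2 = b) over all pairs with |a − b| ≥ k.

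| p | k = 3 (20 points) | k = 5 (33 points) |
|---|---|---|
| 0.3 | 0.318 | 0.071 |
| 0.5 | 0.362 | 0.099 |
| 0.7 | 0.318 | 0.071 |

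These are for one pair of arms. The chance that at least one of the three pairs differs by 3 or more is 0.575 at p = 0.3 or 0.7, and 0.630 at p = 0.5. For a continuous score, the standard error of a baseline mean difference is √(2/15) = 0.37 SD.

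**4. Precision gained by adjustment (illustration).** Assumptions: a continuous score, baseline correlation r, two-sided alpha 0.05, 80% power, one pair of arms, no multiplicity correction, normal approximation. Residual variance is 1 − r² of the unadjusted variance. The detectable difference without a baseline is (1.960 + 0.842) × √(2/15) = 1.02 SD, and adjustment multiplies it by √(1 − r²).

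| r | Variance reduction | Detectable difference | Power at 0.8 SD |
|---|---|---|---|
| No baseline | – | 1.02 SD | 59% |
| 0.3 | 9% | 0.98 SD | 63% |
| 0.5 | 25% | 0.89 SD | 72% |
| 0.7 | 49% | 0.73 SD | 87% |

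**5. Size of the resolution analysis.** The expected number symptomatic at entry per arm is 15 × 0.3 = 4.5 to 15 × 0.7 = 10.5.

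**The case against.** The strongest reply is that Aim 2 does not need a baseline. Both hypotheses are comparisons with control in a randomised, double-blind trial. On-treatment status can be compared without bias, the error rate of the test already allows for chance imbalance, and symptoms that resolved before enrolment are expected equally in every arm. This stands. A reader might infer that the missing baseline biases the comparison, or makes Aim 2 untestable. The documents support neither. Precision, a check on imbalance and a defined starting group for resolution are what is lost.

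A second reply is that some symptoms do have pre-spray data. This also stands: smell is the subject of Hypothesis 2b, and the Day 1 and Day 30 smell tests allow change to be measured. It would be wrong to say that all symptom data are on treatment.

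A third is that the precision figures assume a continuous score and a baseline correlation, whereas the plan names neither and intends a chi-square test. This is correct, so the figures in step 4 are illustrative, and at r = 0.3 the gain is small. Nor can on-treatment status be called mainly a reflection of starting severity: the documents give no severity distribution or correlation. Entry of inpatients and outpatients makes variation plausible, but does not measure it.

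Finally, the intake form is only summarised, so it may hold items that are not listed. If it does, the protocol should say so.

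**Conclusion.** The point holds for fever, fatigue, nasal congestion and sore throat. No version of the schedule places a symptom form before the first spray, and the intake questionnaire is not listed as recording presence or severity of these symptoms. It does not hold for smell and taste.

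The randomised comparison remains valid. Its weakness is that an entry imbalance of 3 or more participants between two arms, expected in 32 to 36% of randomisations at an assumed prevalence of 30 to 70%, would go unseen and uncorrected. Time to resolution is the part of Aim 2 most affected, because no one is documented as having the symptom at the start. The precision gain from a baseline ranges from 9% to 49% of variance over assumed correlations of 0.3 to 0.7, for a continuous score only.

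The trial's primary outcome, viral load, has a pre-spray sample and is not affected. The change is worth making because it is nearly free and the value cannot be reliably recovered later.

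**What to change.** - **Collection.** Have participants complete the same REDCap symptom form at the enrolment visit, before the first spray, alongside the intake questionnaire. Add it to Measurements/Outcomes and to the timeline.
- **Schedule.** When making this change, reconcile the three descriptions of form frequency and the Day 0/Day 1 numbering.
- **Comparison of symptoms.** In place of an unadjusted chi-square, adjust the on-treatment comparison for the baseline value: logistic or ordinal regression for presence or grade, or ANCOVA if a score is used.
- **Time to resolution.** Analyse it among participants who had the symptom at baseline. Keep the comparison of presence or severity in all randomised participants alongside.

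The cost is a few minutes of participant time and short additions to the text. The resolution analysis will rest on fewer participants, about 4.5 to 10.5 expected per arm at the assumed prevalences, so it should be presented as descriptive or low-powered. The precision gain from adjustment may be small if the baseline correlation is low.
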